6. STUDY PHASES FROM SCREENING TO END OF STUDY

6.1. Screening

As part of the screening visit, study center personnel will explain to the potential patient all aspects of the study, obtain signed informed consent, and document the informed consent process in the patient's source documents before any study-specific procedures are conducted.

The signed ICF initiates screening that must occur within 28 days of enrollment (Day -28 to Day -1). Study center personnel will access the Interactive Response Technology (IRT) system to obtain a screening identification number for the potential patient, which is generated by IRT.

Required screening assessments, some with shorter screening windows, are listed in [Appendix 1](#). Assessments obtained within 14 days of Day 1 (pregnancy and laboratory assessments: within 7 days

of Day 1) do not have to be repeated on Day 1. Results of standard of-care tests or examinations performed before obtaining informed consent and within the screening windows may be used and do not have to be repeated as long as they meet protocol specifications.

It is highly recommended that general screening assessments such as physical examination and laboratory assessments should be conducted first to rule out ineligibility based on those grounds before more involved and/or invasive procedures are carried out.

The investigator must assess the potential patient for eligibility. Screen failures and consent withdrawals must be documented in the patients' source documents.

6.2. Enrollment

After determination of eligibility, the investigator will complete the treatment authorization form and supporting documentation and provide them to the sponsor and/or designee for review and subsequent approval. No eligibility waivers will be granted.

6.3. Treatment

Day 1 of Cycle 1 is the first day of any study treatment administration (there is no Day 0 in this protocol).

Details on study treatment are provided in [Section 7.1](#).

Study procedures of each clinic visit are outlined in [Appendix 1](#).

On days with PK assessments, study drug should be administered in the clinic in accordance with the schedule for the PK samples. Assessments should be obtained before study drug administration unless stated otherwise in [Appendix 1](#) and should be performed in order of least invasive to most invasive assessment. All safety-related assessments must be reviewed and dose modifications, if necessary, be made by the investigator or subinvestigator before study drug administration.

6.4. Unscheduled Visit

Unscheduled visits may occur any time as necessary as per investigator decision or patient's request for reasons such as additional assessment or follow-up of AEs. If PD is suspected an MRI should be performed

6.5. Permanent Discontinuation of Study Treatment

6.5.1. Reasons for Permanent Discontinuation of Study Treatment

Patients may permanently discontinue study treatment for any of the following reasons:

- Disease progression
- Adverse event(s)
- Death

- Pregnancy
- Major protocol deviations
- Patient withdrew consent for study treatment
 - Patients may voluntarily withdraw consent from study treatment at any time
 - If a patient withdraws consent from the Treatment Phase they should continue with all follow-up visits including survival follow-up
- Start of other anticancer therapy

Other than for treatment completion (Arms A and B), the reason for discontinuation from treatment will be recorded on the electronic case report form (eCRF). Every effort must be made to encourage the patient to complete their EOT visit and appropriate safety follow-ups.

6.5.2. End of Treatment Visit

Patients in Arms A and B who have completed all study treatments per protocol and do not continue on pamiparib in combination with TMZ will have their EOT visit at the end of the Rest Phase, 28 days after RT was completed. Patients continuing on pamiparib in combination with TMZ (maintenance) should follow the schedule of assessments for maintenance treatment ([Appendix 1 Table 4](#)).

All other patients with any of the reasons for discontinuation of study treatment listed above will undergo an EOT visit within 7 days after stopping all study treatments.

A visit should be scheduled as soon as possible, but the EOT visit may occur later after discussion with the medical monitor for specific circumstances, such as prolonged hospitalization. The visit at which MRI showed PD may be used as the EOT visit provided that all required assessments were performed. MRI does not have to be repeated if it was performed within 14 days of the EOT visit or at a prior response evaluation that documented PD. ECG does not have to be repeated if it was performed within 14 days of the EOT visit.

6.6. Follow-Up Phase

6.6.1. Safety Follow-Up

Approximately 30 days after the last day of study drug or before initiation of new anticancer therapy, whichever occurs first, a safety follow-up will occur with the safety assessments outlined in [Appendix 1](#). If new anticancer therapy is inadvertently initiated before this safety follow-up (eg, without the knowledge of the study center team), a safety follow-up should be scheduled as soon as possible.

6.6.2. Efficacy Follow-Up

Patients who were not discontinued from study treatment due to PD and meet criteria otherwise (eg, discontinued for AE and no new anticancer therapy) will be followed every 8 weeks (± 7 days) until

disease progression, administrative issues, start of other anticancer therapy or any other reason listed in [Section 6.7](#), whichever occurs first.

For efficacy assessments as per protocol, refer to [Section 8.3](#) and [Appendix 1](#). If the patient refuses to return for these visits or is unable to do so, every effort should be made to contact the patient or patient's guardian by telephone to determine the patient's disease status and survival.

6.6.3. Survival Follow-Up

Patients will be followed for survival and further anticancer therapy information post progression via phone contact or other means (with the patient's guardian, if applicable) approximately every 12 weeks as per [Appendix 1](#).

6.6.4. Lost to Follow-Up

If attempts to contact the patient by phone are unsuccessful, the following additional attempts should be made to obtain protocol-required follow-up information. The patient should be contacted by mail in a manner that provides proof of receipt by the patient. If unsuccessful, other contacts should be explored, such as referring physicians or relatives. Attempts of contact should be documented in the patient's source documents. If a patient cannot be contacted despite all attempts, the patient will be considered lost to follow-up, and death information should be obtained through a public record search if local agencies permit.

6.7. End of Study

Premature discontinuation from the study without EOT and any follow-up visits may occur under the following circumstances:

- Patient withdrew consent for study participation
 - Patients may voluntarily withdraw consent from the study at any time.
- Investigator's discretion
- Lost to follow-up
 - The investigator should show due diligence by documenting in the source documents steps taken to contact the patient, eg, dates of telephone calls or registered letters ([Section 6.6.4](#))
- Death
- Study termination by sponsor
- Other, as per the discretion of the sponsor or health authority

7. STUDY TREATMENT

7.1. Study Treatments

7.1.1. Pamiparib

7.1.1.1. Packaging and Labeling

Pamiparib capsules are provided in a container with a child-resistant closure. Patients will receive pamiparib as 20 mg or 60 mg capsules, depending on dose level and availability. The contents of the label will be in accordance with all applicable local regulatory requirements. The label will include at a minimum: drug name, dose strength, contents, sponsor, protocol number, batch number, directions for use, storage conditions, caution statements, retest or expiration date, and space to enter the patient number, visit number, and name of investigator.

7.1.1.2. Handling and Storage

The instructions for drug ordering are in the Pharmacy Binder. The IRT system will also be used for drug supply management. The study drug will be dispatched to a study center only after receipt of the required documents in accordance with applicable regulatory requirements and the sponsor's procedures. The investigator or pharmacist/designated personnel is responsible for maintaining the drug supply inventory and acknowledging receipt of all study drug shipments. All study drugs must be stored in a secure area with access limited to the investigator and authorized study center personnel and under physical conditions that are consistent with study drug specific requirements.

Pamiparib must be kept at 15°C to 30°C (59°F to 86°F) and protected from light. An accurate study drug accountability log must be maintained and kept up to date at all times.

7.1.1.3. Dosage and Administration

Pamiparib 60 mg will be administered PO BID, once in the morning and once in the evening. The time difference between 2 consecutive doses should be approximately 8 to 12 hours.

Patients will be instructed to swallow the capsules whole, in rapid succession, with water. Patients will be required to fast for at least 1 hour before and 2 hours after each pamiparib administration. Water is allowed during the fasting period.

A dose of pamiparib should be skipped if it is not taken within 2 hours of the scheduled time. An extra dose of pamiparib should not be taken to make up for a missed dose. If vomiting occurs during the course of treatment, no re-dosing of the patient is allowed before the next scheduled dose.

On days with PK assessments, the morning dose of pamiparib should be administered in the clinic in accordance with the schedule for PK samples ([Appendix 1](#)).

7.1.2. Temozolomide

7.1.2.1. Packaging and Labeling

Capsules of TMZ are available in 20 and 100 mg. Please refer to the package insert for detailed information.

7.1.2.2. Handling and Storage

Please refer to the package insert for detailed information.

7.1.2.3. Dosage and Administration

Temozolomide will be administered PO QD, preferably during the same time frame each day (ie always in the morning or always in the evening). The daily dose and schedule will be determined by arm and stage of study as outlined in [Section 4.2.1](#).

On days with PK assessments, TMZ should be administered in the clinic.

Patients will be instructed to swallow the capsules whole, in rapid succession, with water.

A dose of TMZ should be skipped if it is not taken within 2 hours of the scheduled time. An extra dose of TMZ should not be taken to make up for a missed dose. If vomiting occurs during the course of treatment, no re-dosing of the patient is allowed before the next scheduled dose.

Antiemetic prophylaxis is usually not required for TMZ. However, prophylaxis with a 5-HT₃ antagonist is recommended prior to administration of the first few TMZ doses and should be administered orally 30 to 60 minutes before TMZ treatment. Most patients report optimal nausea control with the use of a 5-HT₃ antagonist. If optimal nausea control cannot be achieved, any alternative dosing schedule, such as TMZ administration at night, should be discussed with the medical monitor before implementation.

For patients receiving TMZ (Arms B & C), *Pneumocystis jirovecii* pneumonia prophylaxis is required as outlined in [Section 7.2.2](#).

7.1.2.4. Temozolomide and Pamiparib Drug-drug Interaction Potential

Temozolomide is spontaneously hydrolyzed at physiologic pH to the active species, 5-(3-methyltriazene-1-yl) imidazole-4-carboxamide (MTIC) and to temozolomide acid metabolite. MTIC is further hydrolyzed to 5-amino-imidazole-4-carboxamide (AIC), which is known to be an intermediate in purine and nucleic acid biosynthesis, and to methylhydrazine, which is believed to be the active alkylating species. Cytochrome P450 enzymes play only a minor role in the metabolism of temozolomide and MTIC (USPI).

CYP phenotyping study using human liver microsomes with selective CYP inhibitors and recombinant CYP enzymes suggests that CYP3A was the major CYP isoform responsible for pamiparib metabolism while CYP2C8 contribute to pamiparib metabolism to a lesser extent. Pamiparib is a moderate inhibitor for CYP2C9 (IC₅₀ = 6.48 μM) while its IC₅₀ for other CYP

isozymes are all greater than 10 μ M. Pamiparib is not a time-dependent CYP inhibitor of the 7 major CYP isozymes tested (please see the [Pamiparib IB](#)).

Consequently, the drug-drug interaction potential between pamiparib and TMZ is believed to be low when coadministered.

7.1.3. Radiation Therapy

All patients in Arms A and B will receive RT using either standardized 3-dimensional conformal radiotherapy (3DCRT) technique, intensity modulated radiotherapy (IMRT), volumetric modulated arc therapy (VMAT) or other 3D conformal technique on a linear accelerator delivering a beam energy of ≥ 6 MV. Radiation therapy, associated 3D radiation therapy planning and stabilization/immobilization procedures will be performed as per local guidelines and taking into account local institutional standard of care.

Patients will receive radiation therapy 5 days per week, in once daily fractions, 1.8 or 2 Gy per fraction, to a total target dose between 58 Gy and 64 Gy in 29 to 33 fractions, for a total duration of up to 7 weeks. The radiation dose should be prescribed to the tumor and its immediate surrounding tissue abnormalities.

Treatment planning should ideally be carried out based on results of the MRI. The target volume should at a minimum encompass the contrast-enhancing lesion (and/or surgical cavity) on T1-weighted post-contrast MRI and an acceptable margin, and may include surrounding tissue abnormalities as demarcated on T2w or FLAIR MR images.

Target Volumes

Recognizing variation in target volume definitions exists, the definition of volumes will be in accordance to recognized standard and local guidelines with appropriate reference to the European Society for Radiotherapy and Oncology (ESTRO)-Advisory Committee on Radiation Oncology Practice (ACROP) guideline for “Target delineation of Glioblastomas” ([Niyazi et al, 2016](#)) and the American Society for Radiation Oncology (ASTRO) Evidence-Based Clinical Practice Guideline “Radiation Therapy for Glioblastoma” ([Cabrera et al, 2016](#)).

North American radiation oncology cooperative groups generally treat patients in 2 phases, with an initial phase directed at edema (hyperintense region on T2/FLAIR on MRI) in addition to the resection cavity and gross residual tumor (enhancing lesion on T1) followed by a boost directed only at the resection cavity and gross residual tumor. T2 hyperintense regions are targeted in this paradigm because of evidence that T2 hyperintensity sometimes reflects infiltrative and/or low-grade tumor. Some institutions, however, utilize a two-phase treatment paradigm targeting resection cavity and gross tumor alone without specifically targeting edema, citing similar patterns of failure with this approach. ([Cabrera et al, 2016](#)). Institutional standards may consist of delivery of a simultaneous integrated boost (SIB) that targets the T2w/FLAIR hyperintense regions and T1w contrast enhancement and resection cavity at the same time.

The European Organization for Research and Treatment of Cancer (EORTC) has adopted a single-phase approach, targeting the enhancing tumor plus cavity with a wide margin throughout the entire treatment, without specifically targeting edema. (Niyazi et al, 2016).

The following are recommendations for target volume definitions.

Gross tumor volume

The gross tumor volume (GTV) is defined by:

- The region of enhancement (without oedema) on post-operative CT/ T1-weighted MRIs (if available) or the region of enhancement (without oedema) on pre-operative CT/T1-weighted MRIs if post op imaging is not available (usually contained in the above),

Plus

- The tumor resection margin (usually contained in the above)

In some tumors no area of enhancement can be seen and the GTV is defined entirely on the T2 abnormality.

For newly diagnosed GBM and in case of complete or subtotal removal, the position of the tumor bed can have shifted, and the GTV should take the new position of the abnormalities on the planning CT scan and any post-operative imaging into account. Post-operative imaging is not mandatory, and it is acceptable to define GTV based on preoperative scans and a planning CT, the latter ideally with IV-contrast.

Clinical target volume

The clinical target volume (CTV) is defined as the GTV plus a margin to account for microscopic spread. This will usually be in the order of 2 to 3 cm but should include all areas of persisting oedema (T2 weighted area on MRI/hypo dense area on CT), but can be reduced in anatomical regions where spread is unlikely (eg, below the tentorium cerebelli) and keeping the volume within the skull.

The CTV extends to the contralateral hemisphere only when midline structures such as the corpus callosum and the contralateral hemisphere are invaded by tumor. The tentorium and meninges should be considered as anatomical borders and therefore a margin of 3-10 mm is sufficient to encompass the microscopic spread at these borders, always keeping the volume within the outer table of the skull.

Planning target volume

The planning target volume (PTV) will provide a margin around the CTV to compensate the uncertainties of the setup and the delivery. This margin should be based upon known individual departmental evaluations. In case it was not investigated the PTV should be defined as CTV plus 3-5 mm margins to all directions. To ensure that surface dose inaccuracies of the treatment planning

system are avoided, the PTV border should be collapsed to inside the natural barriers by limiting to 3 mm from the skin surface.

Additional target volumes and cone downs as and if defined per local standards.

Organs at Risk

To minimize radiation exposure, organ(s) at risk, including eyes, optic nerves, optic chiasm, left and right cochlea, brain stem, and normal brain should be contoured during treatment planning. Every attempt should be made to shield the contoured organs at risk during radiotherapy planning to minimize their dose after satisfying planning requirements for the respective volumes. The maximum administered doses to the organ at risk must be as follows ([Scottianti et al, 2015](#)):

Organ at Risk	Maximum Dose (Gy)
Lenses	7
Optic nerves/Optic chiasma	56
Cochlea	≤ 45 (< 34 to contralateral cochlea)
Brainstem	60
Retina	< 45
Lacrimal gland	< 40

The maximal dose to non-specified normal tissues, such as skin and any uninvolved brain hemisphere, is 105% of the prescription dose.

Compliance Criteria

Radiation therapy will be given regardless of the administration of pamiparib (Arm A) and pamiparib in combination with TMZ (Arm B). For example, if administration of pamiparib and/or TMZ has been modified or delayed due to toxicity related to study drugs only, RT may continue.

Interruptions in RT that may be necessitated by skin reaction, brain edema, or other acute reactions are permitted for up to a total of 7 days but the reason for the interruption should be clearly documented in the patient chart and CRF. For interruptions of 8 days or greater, a deviation will be assigned.

For additional details, please see the study Radiation Manual.

7.1.4. Radiation Therapy Adverse Events

Toxicities arising during or after the completion of radiation therapy and attributed to radiation will be assessed according to NCI-CTCAE v4.03 criteria.

7.1.4.1. Acute

Expected acute radiation-induced toxicities include hair loss, fatigue, and erythema or soreness of the scalp. Potential acute toxicities include nausea and vomiting as well as temporary aggravation of brain tumor symptoms such as headaches, seizures, and weakness. Reactions in the ear canals and on

the ear should be observed and treated symptomatically; these reactions could result in short-term hearing impairment. Dry mouth or altered taste have been occasionally reported.

7.1.4.2. Early Delayed

Possible early delayed radiation effects include lethargy and transient worsening of existing neurological deficits occurring 1-3 months after radiotherapy treatment.

7.1.4.3. Late Delayed

Possible late delayed effects of radiotherapy, typically occurring >3 months after completion of RT, include radiation necrosis, endocrine dysfunction, and radiation-induced neoplasms. In addition, neurocognitive deficits, which could lead to mental slowing and behavioral change, are possible. Permanent hearing impairment and visual damage are rare. Cataracts can be encountered.

7.1.5. Dose Holds and Modifications of Study Treatments

7.1.5.1. General Considerations for Modifications of Study Treatments

AEs should be assessed as best as possible regarding their relatedness to one or more study treatment(s). Investigators should discuss potential dose modifications with the medical monitor prior to implementation, if feasible. Regardless of discontinuation of one, two or all study treatment(s), patients should continue on study with regular follow-up as outlined in [Section 6.5.2](#) and [Section 6.6](#).

Patients who experience a DLT during the DLT assessment window, or a clinically significant Grade 2 toxicity or Grade 3 or 4 toxicity considered related to study treatment after the DLT assessment window, may temporarily suspend study treatment. Depending on the toxicity, study treatment may resume within 28 days after discussion with the medical monitor.

Dosing of pamiparib and TMZ can be interrupted for approximately 28 days for medical events that are not associated with toxicity related to these study drugs or disease progression.

Criteria for treatment modifications and suggested guidelines for the management of toxicities related to pamiparib and/or TMZ are summarized below. These general guidelines may be modified at the discretion of the investigator based on best clinical judgement at that time. Any toxicities related to pamiparib and/or TMZ should be managed according to standard medical practice.

Once a dose of pamiparib or TMZ has been reduced, re-escalation is not allowed.

7.1.5.2. Dose Modification Considerations for Combinations with Radiation Therapy

For the patient populations of Arms A and B, RT is an important cornerstone of treatment and should not be compromised because of administration of pamiparib and/or TMZ. Consequently, **RT should only be modified for AEs determined to be solely or mostly related to RT as typically done per standard of care.**

If AEs are encountered that are considered related to pamiparib and/or TMZ, dosing modifications for pamiparib and/or TMZ should be implemented as outlined in [Table 3](#) and [Table 4](#).

If RT is temporarily interrupted for reasons unrelated to pamiparib and TMZ (if applicable), then treatment with pamiparib and TMZ should continue as scheduled. If RT is permanently interrupted for reasons unrelated to pamiparib and TMZ (if applicable), the investigator may consult the medical monitor on the appropriateness of initiating maintenance treatment with pamiparib and TMZ.

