4.2. Details of Dose-Escalation Stage

4.2.1. Starting Dose and Dose-Escalation Approach

Arm A

RT will be administered QD × 5 days/week for 6 to 7 weeks with 1.8 or 2 Gy/fraction for a total target dose of between 58 Gy and 64 Gy.

The starting dose for pamiparib will be the 60 mg PO BID based on the rationale outlined in [Sections 1.3](#) and [1.4](#). In Cohort 1, exposure to pamiparib will be limited to the first 2 weeks of RT. In Cohorts 2 and 3, pamiparib will be given for the first 4 and 6 weeks of RT, respectively. If 2, 4, or 6 weeks of combination treatment exceeds the MTD, alternative regimens for pamiparib may be explored after discussions with all investigators based on which regimen exceeded the MTD and

what toxicities were observed. For example, if 2 weeks of pamiparib are not tolerated, a schedule of 1 week on, 1 week off, or 1 week on and 3 weeks off may be explored. Depending on data available at that time, a lower dose level of pamiparib may also be explored.

Arm B

The opening of Arm B will depend on the safety of the Arm A combination, and Arm B may be enrolled at the initial dose and schedule of pamiparib found to be safe and tolerable in Arm A. RT will be administered as for Arm A.

The first dose level of TMZ will be lower than or equal to a dose that has been determined to be safe and tolerable in Arm C, and dose escalation will proceed as described for Arm C. The time period of TMZ administration may be the same or shorter than that for pamiparib administration. Similar to Arms A and C, alternative regimens may be explored with adjustments of dose and/or schedule as outlined for Arms A and C.

Arm C

Since TMZ is given as a DNA-damaging sensitizer for pamiparib and to simplify TMZ dosing, flat-dosing will be used for TMZ. The first dose level of 40 mg QD corresponds to 23 mg/m^2 assuming an average body surface area of 1.73 m^2 . Subsequent dose levels of 80 mg and 120 mg correspond to 46 mg/m^2 and 69 mg/m^2 , respectively. Additional higher dose levels may be explored, and the TMZ dose will not be increased by more than 50% each time. TMZ will be given on Days 1 to 21 of each 28-day cycle based on data and rationale discussed in [Sections 1.2, 1.3, and 1.4](#).

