4.2.3. Assessment of Dose-Limiting Toxicity

Dose-limiting toxicities will be assessed during the DLT assessment window starting with the first day of study treatments for all cohorts. The following assessments must be obtained at the end of the DLT assessment window: complete physical examination, vital signs and weight, Eastern Cooperative Oncology Group (ECOG) performance status, ECG, hematology, chemistry, coagulation, urinalysis, AEs, and concomitant medications.

For Arm A, the DLT assessment window will depend on the time period of pamiparib administration during RT and will consist of the time period of combination treatment plus 4 weeks after the last scheduled combination treatment, eg, 6 weeks for Cohort 1 of Arm A when pamiparib is given during the first 2 weeks of RT, and 10 weeks for Cohort 3 of Arm A when pamiparib is given during 6 weeks of RT.

For Arm B, the DLT assessment window will depend on the time period of combined administration of pamiparib and TMZ during RT and will otherwise follow Arm A rules, eg, if TMZ will be given only for the first 3 weeks of pamiparib and RT, then the DLT assessment window will be 7 weeks.

For Arm C, the DLT assessment window will encompass the first cycle of 28 days.

Patients who withdraw or are withdrawn from the study prior to completing the DLT assessment window for reasons other than a DLT will not be considered evaluable for DLT and will be replaced if needed to meet patient number requirement for dose escalation. Patients who do not experience a DLT and who do not receive ≥ 42 Gy of RT (Arms A and B) and $\geq 70\%$ of scheduled pamiparib (Arms A, B and C) and TMZ (Arms B and C) dosing during the DLT assessment window will not be considered evaluable for DLTs and will be replaced if needed to meet patient number requirement for DLT assessment.

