6 STATISTICAL METHODS

6.1 ANALYSIS POPULATIONS

Safety Analysis Set: includes all patients who received any dose of any of the study treatments (pamiparib, RT and/or TMZ). The Safety Analysis Set will be used for efficacy and safety analyses.

Efficacy Analysis Set: includes all patients in the Safety Analysis Set who:

Arms A & B: had a tumor assessment at baseline and at End of Treatment unless discontinued treatment or study early due to disease progression or death prior to tumor assessment.

Arm C: had measurable disease at baseline and at least one postbaseline tumor assessment unless discontinued treatment or study early due to disease progression or death prior to tumor assessment.

DLT-Evaluable Analysis Set: includes patients from escalation cohorts only in the Safety Analysis Set who received ≥ 42 Gy of RT (Arms A and B) and $\geq 70\%$ of scheduled pamiparib (Arms A, B and C) and TMZ (Arms B and C) during the DLT assessment window. All patients who had a DLT event will be considered DLT-evaluable regardless of study treatment intensity.

PK Analysis Set: includes all patients for whom valid pamiparib PK parameters can be estimated.

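### DLT evaluability in Arms A and B counts RT and drug separately and never tests their overlap, so after a short combination period a patient can be evaluable and DLT-free on about half the planned combination

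*Protocol*

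**What the plan says.** Protocol 4.2.1 sets the Arm A escalation steps by duration of combined treatment. "In Cohort 1, exposure to pamiparib will be limited to the first 2 weeks of RT"; Cohorts 2 and 3 extend this to 4 and 6 weeks. SAP 3.1.1 states the same aim by adding length of treatment to the Arm A objective.

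Protocol 4.2.3 sets the DLT window as the combination period plus 4 weeks. It then gives two exposure conditions for DLT-free patients: at least 42 Gy of RT (Arms A and B), and at least 70% "of scheduled pamiparib (Arms A, B and C) and TMZ (Arms B and C) dosing during the DLT assessment window". A DLT-free patient who falls short of this "dosing during the DLT assessment window will not be considered evaluable for DLTs and will be replaced if needed". Protocol 11.2.1 repeats the thresholds. SAP 6.1 does too, restricted to escalation cohorts ("DLT-Evaluable Analysis Set: includes patients from escalation cohorts only in the Safety Analysis Set who received" the stated amounts), and adds the usual protection: "during the DLT assessment window. All patients who had a DLT event will be considered DLT-evaluable regardless of study treatment intensity".

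Two other sections decide whether RT and drug coincide. Protocol 7.1.5.2: "If RT is temporarily interrupted for reasons unrelated to pamiparib and TMZ (if applicable), then treatment with pamiparib and TMZ should continue as scheduled". Protocol 7.1.3 says that RT interruptions for skin reaction, "brain edema, or other acute reactions are permitted for up to a total of 7 days"; 8 days or more is recorded as a deviation, and no section removes such a patient from the DLT set.

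**The concern.** In Arm A the quantity being escalated is concurrent exposure, so a DLT-free patient is informative about a step only if most of that step's concurrent exposure was received. The evaluability rule does not check this. The 42 Gy condition is a whole-course amount (70% of a 60 Gy course) and, in a short-combination cohort, most of it can be delivered after pamiparib has stopped. The 70% drug condition does not close the gap, because the drug runs on through an RT pause and is fully credited.

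Protocol 4.2.2 lets escalation proceed on none of three, or fewer than two of six, evaluable patients with a DLT. With so few patients, one who had half the planned combination and is counted as DLT-free can make a step look better tolerated than was shown. The Arm A exposure is then carried into Arm B.

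**Working it through.** **Inputs.** RT is 5 fractions per week at 1.8 or 2 Gy, 58-64 Gy in 29-33 fractions (Protocol 4.2.1, 7.1.3). The window is combination weeks + 4 (4.2.3). The permitted pause is 7 days (7.1.3). Assumptions: 7 days means consecutive calendar days, so 5 treatment days; the pause falls wholly inside the combination period; missed fractions are made up at the end; pamiparib is taken as scheduled.

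**Reproducing the plan's windows.** Cohort 1: 2 + 4 = 6 weeks. Cohort 3: 6 + 4 = 10 weeks. Arm B example: 3 + 4 = 7 weeks. All agree with 4.2.3.

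**Overlap after a permitted pause.** Planned concurrent fractions = 5 × combination weeks; after the pause, subtract 5.

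| Setting | Planned | After pause | Share |
|---|---|---|---|
| Arm A Cohort 1 (2 wk) | 10 | 5 | 50% |
| Arm B example (3 wk) | 15 | 10 | 67% |
| Arm A Cohort 2 (4 wk) | 20 | 15 | 75% |
| Arm A Cohort 3 (6 wk) | 30 | 25 | 83% |

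**Does the Cohort 1 patient still qualify?** The 6-week window holds 5 × 6 = 30 fraction slots. 30 - 5 = 25 fractions, which is 25 × 1.8 = 45 Gy or 25 × 2 = 50 Gy. Both exceed 42 Gy and pamiparib is 100%, so the patient is evaluable. In the Arm B example, 35 - 5 = 30 slots remain (54-60 Gy), so that patient qualifies too.

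**What 42 Gy guarantees by itself.** The 4 weeks after the combination hold 20 slots: 36 Gy at 1.8 Gy or 40 Gy at 2 Gy. Fractions needed for 42 Gy: 24 (24 × 1.8 = 43.2) or 21 (21 × 2 = 42). The guaranteed concurrent minimum is 24 - 20 = 4 or 21 - 20 = 1. Getting that low in Cohort 1 means missing 6 or 9 concurrent fractions, more than a permitted 7-calendar-day pause.

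**If 7 days meant 7 treatment days.** Cohort 1: 3 of 10, with 23 fractions in the window. That is 46 Gy at 2 Gy (evaluable) but 41.4 Gy at 1.8 Gy (not evaluable). Cohort 2: 13/20 = 65%. Cohort 3: 23/30 = 77%.

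**Illustration of the effect on escalation (assumed risks, not in the documents).** With DLT probability p for every patient, P(pass) = (1-p)³ + 3p(1-p)⁵. At p = 0.33 this is 0.301 + 0.134 = 0.434. If one of the first three patients has half that risk (0.165), P(no DLT in 3) = 0.835 × 0.67² = 0.375, P(one DLT) = 0.165 × 0.67² + 2 × 0.33 × 0.67 × 0.835 = 0.443, and P(pass) = 0.375 + 0.443 × 0.67³ = 0.508. At a quarter of the risk it is 0.545. If instead each of six patients independently has a 5% or 10% chance of being at half risk, the average p is 0.33 × (1 - 0.025) = 0.322 or 0.33 × (1 - 0.05) = 0.3135, and P(pass) is about 0.45 or 0.47.

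**The case against.** **The sections do not contradict one another.** Continuing pamiparib through an unrelated RT pause is part of the regimen, and an overlap cutoff is a reviewer's choice. That is fair: this is a gap in an analysis-set rule, not an inconsistency. But the plan already requires 70% of scheduled drug, and it applies no comparable standard to the quantity that Arm A escalates.

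**A reader might infer that 42 Gy is the only requirement, or that 1 of 10 concurrent fractions is an ordinary outcome.** Neither is supported. The drug criterion stands beside the RT criterion. The 1-of-10 floor applies only at 2 Gy and needs nine missed concurrent fractions, a deviation-length interruption. The 3-of-10 case needs both 2 Gy fractions and a treatment-day reading of the 7-day limit.

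**A reader might infer that the recommended Arm A schedule is unsound.** The documents do not support that. Cohorts 2 and 3 keep 75% and 83% under a permitted pause, and a wrongly passed Cohort 1 leads to a Cohort 2 that is tested in its own patients. Escalation after 0 of 3 is optional and goes through a team review (Protocol 4.2.2), and RT interruption reasons are documented, so a paused patient can be noticed.

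**The risk model is assumed.** This stands. A DLT must be judged related to pamiparib (Protocol 4.2.4), and pamiparib alone produced DLTs in the first-in-human study (Protocol 1.3.5.3). A patient on full pamiparib may therefore keep much of the risk. The frequency of early pauses is not given.

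**Selective loss of overlap in patients with radiation reactions is possible but weak.** Protocol 10.1.3 counts an event as related when a causal link cannot be excluded. A qualifying severe reaction would often be a DLT, and that patient stays evaluable whatever the exposure.

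**Conclusion.** The gap is real and limited. Neither document links RT and drug timing in DLT evaluability. In Arm A Cohort 1, a permitted 7-calendar-day pause in weeks 1-2 leaves 5 of 10 concurrent fractions in a patient who still counts as evaluable and DLT-free, at either fraction size. The Arm B example drops to 10 of 15. Longer combination periods stay at 75% or more if drug is taken as scheduled. The documents show neither that such patients occurred nor that an escalation decision would have differed. The rise in pass probability from 43% to 51-55% is conditional on one affected patient among the first three and on invented risks; with affected patients at 5-10% it is about 45-47%. The point is worth correcting because the remedy is cheap and concerns who is counted, not how anyone is treated.

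**What to change.** **Protocol 4.2.3 and 11.2.1.** For DLT-free patients, keep both existing thresholds and add a minimum share of the RT fractions scheduled in the combination period (pamiparib in Arm A, pamiparib + TMZ in Arm B). A value of 70% would match the drug criterion: 7 of 10, 14 of 20 or 21 of 30 in Arm A Cohorts 1 to 3, and 11 of 15 in the Arm B example (0.7 × 15 = 10.5, rounded up). Patients with a DLT remain evaluable regardless. The definition should also say whether the 7-day limit in 7.1.3 means calendar or treatment days.

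**SAP.** Section 5 reports Phase 1b enrolment as final at 46 patients, so replacement is no longer available, and redefining the set now would detach the report from the decisions taken. Keep the DLT set used for escalation in 6.1. List planned and received concurrent fractions for each DLT-evaluable patient in Arms A and B, and repeat the 6.5.2 DLT table without DLT-free patients below the threshold.

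**Cost.** In a continuing escalation, an occasional patient is not evaluable and is replaced. In the SAP, the cost is one listing, one repeated table and a slightly smaller sensitivity set. Protocol 11.3.1 promises listings of all dosing records and 7.1.3 requires RT interruption reasons on the CRF, but neither expressly mentions fraction dates, so confirm that these can be extracted. The dosing rule in 7.1.5.2 is untouched.
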